# 4.5. Secondary Aim 1: To compare the severity of recurrence of Hepatitis C between LDLT and DDLT recipients.

1134 1135

1136 Hepatitis C virus (HCV) infection is the most common indication for DD and live donor 1137 liver transplantation in North America. Reinfection of the graft is universal in patients 1138 who are viremic pre-transplantation and recurrent disease is more rapidly progressive 1139 post-transplantation than in the non-transplant setting. Among DDLTs, graft survival is 1140 reduced for patients with HCV disease compared to patients with other causes of chronic 1141 liver disease except malignancy. Chronic rejection, recurrent malignancy and recurrent 1142 HCV are the most common causes of late graft loss. Factors most consistently associated 1143 with progressive disease and recurrent cirrhosis: are year of transplantation, donor age, 1144 pre-transplant level of viremia, absence of HBV coinfection and acute rejection.

1145

1146 Preliminary studies of LDLT recipients suggest that allograft injury due to HCV occurs

earlier and is more severe compared to recipients of DD livers. In a retrospective study

1148from the University of Colorado and Mount Sinai Hospital in New York, the short-term
Revised Cohort Protocol 031006Page 27 of 56

1149 outcome of 42 LDLT HCV patients was compared to 86 HCV patients undergoing 1150 DDLT. Mean AST and ALT were higher at each follow-up interval reaching statistical 1151 significance at months 1 and 3 for AST and month 1 for ALT. The percentage of patients 1152 with aminotransferase > 100 IU/or bilirubin > 2 mg/dl was higher at each time point for 1153 live donor liver transplant recipients. The time to histologic recurrence was significantly 1154 shorter in live donor recipients (3.5 months) vs. DDLT recipients (6.7 months), (p=0.01) 1155 but protocol biopsies were not performed. While these results suggest that HCV may 1156 recur earlier and be associated with higher serum aminotransferase levels in live donor 1157 liver transplant patients compared to DDLT recipients, the longer term outcomes (risk of 1158 progressive fibrosis and graft loss) are unknown. The current study will examine the rate 1159 and severity of HCV disease in a large prospective cohort of live donor and DDLT 1160 recipients over a 3-year period. Liver biopsies obtained at 3 months and annually will be 1161 compared between groups to assess differences in liver fibrosis and total 1162 necroinflammatory activity, controlling for other factors known to affect disease

- 1163 progression (e.g. donor age, acute rejection episodes, baseline viral level).
- 1164

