118 119 120 121	3.3. Primary Aim 3: To determine the short and long term health and quality of life (QOL) impact of donation, including (a) morbidity after liver donation, and (b) long term health-related QOL of donors compared to a control population.
122 123 124 125 126	
 
To determine the rate of significant morbidity after liver donation.
 
To evaluate long term health-related QOL of donors compared to persons who were evaluated but did not donate.
 

127 128	3.4. Primary Aim 4: To standardize and assess the role of "informed consent" in affecting the decision to donate and satisfaction after living liver donation.
129 130 131 132 133	
 
To measure the capacity of potential donors to understand information that is presented and to stratify the potential donor's capacity to understand information in general and the delivered information regarding the donation in specific.
 
To measure the motivations of the potential donors with standardized
 

133 134 135	instruments and to determine if certain personality characteristics are associated with a more favorable predisposition to proceed to donation.

136 137	3.	To assess whether disclosed information or life situations are the main influential factors in the potential donor's decision to proceed or withdraw
138		from the donation process.
139	4.	To correlate donor "satisfaction" with measurable outcomes of the donor,
140		recipient, or perceptions of family support.
141	5.	To measure the acceptance of adverse clinical outcomes, as a function of
142		understanding of the disclosed risks versus the presence of life situational
143		pressures.
144		
145		econdary Aim 1: To compare the severity of recurrence of hepatitis C
146 147	be	etween LDLT and DDLT recipients.
147	Primary O	bjective
149	1.	To determine whether HCV disease progression differs in patients receiving
150		LDLT compared to DDLT.
151		
152	Secondary	Objectives
153	1.	To determine if recurrent HCV disease at one year ( $\pm$ 3 months), as observed
154		histologically, is more frequent and severe in patients undergoing LDLT as
155		compared to DDLT transplant.
156	2.	To compare the rate of fibrosis progression (change in Ishak fibrosis score (3)
157		per year) in LDLT and DDLT recipients by biopsies at months 3, 12, 24, and
158		36 after transplantation.
159	3.	1 1
160		determined by proportion of patients with histological evidence of recurrent
161		HCV at 3 months.

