162	4.	To determine if HCV viral level at day 7 and months 1, 3, 12, 24 and 36
163		months differ in LDLT and DDLT recipients, and whether viral level is
164	-	predictive of disease severity.
165	5.	J I I C C
166		HCV patients who undergo LDLT as compared to DDLT transplant and to
167		correlate this frequency of treatment of rejection to aggressive recurrence of
168	ſ	HCV as defined histologically.
169	0.	To compare biochemical markers of disease activity (ALT/AST/total
170	7	bilirubin) at 3 and 12 months and annually in LDLT and DDLT.
171	7.	To determine if cholestatic hepatitis in transplanted patients with HCV occurs
172 173	0	in a higher proportion of LDLT as compared to DDLT recipients.
	8.	
174		DDLT recipients.
175		
176	3.6. Se	econdary Aim 2: Recurrence of HCC for DDLT versus LDLT.
177		
178	Primary O	bjectives
170	1	To determine if I DI T is appreciated with deepended doth on writing list from

- To determine if LDLT is associated with decreased death on waiting list from progressive tumor growth versus DDLT.
- 181 2. Assess comparative HCC recurrence following LDLT or DDLT.

Revised Cohort Protocol 031006

182 183 184 185	
 
Compare long-term survival and disease free survival in patients who undergo LDLT or DDLT.
 
Secondary Objectives
 

186 187 188 189 190	
 
Determine if LDLT recipients require a reduced number of palliative ablative procedures to control HCC when compared to those who wait for DDLT.
 
Compare rates of surgical and post-operative complication in HCC recipients of LDLT and DDLT.
 

190 191 192	3.7. Secondary Aim 3: To systematically characterize liver regeneration and function in donors and recipients.
193 194 195 196	Donors and recipients enrolled in the cohort study will be evaluated for evidence of recovery of liver mass and function following the surgical procedures (partial transplantation for recipients of LDLT, and partial hepatectomy for donors).
197 198 199 200 201	In the cohort protocol all donors and recipients of LDLT will undergo standardized assessments of liver volume and function to characterize the rate of restoration of the liver. In the recipient, in which the relative size of the graft will vary based on the unique donor/recipient combinations, the large sample provided in the study will permit us to correlate graft function with a number of donor and recipient parameters.

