202 203 204 205 206 207 208 209	
 
Primary Objective
 
1. To measure hepatic function and mass in living donors at enrollment, intraoperatively, and following hepatectomy, in order to determine whether return of hepatic function following donation correlates with rate of liver volume regeneration, biochemical impairment, and clinical events, and to see whether return of function is complete by 3 months post-resection.
 

210 211 212 213 214 215 216 217 218 219	
 
Secondary Objectives         
 
To correlate liver function in donors with long-term health outcomes and the incidence of clinical complications.
 
To correlate success or failure of regeneration with a series of selected clinical and laboratory variables in donors and recipients.
 
To collect liver biopsy and serum samples prospectively from a large series of donors and recipients which may form the basis for subsequent characterization of protein and gene expression of selected inflammatory and growth-related molecules.
 
 
 

220 221	3.8. Secondary Aim 4: To evaluate differences in the immune response to LDLT vs. DDLT grafts.
222 223 224 225 226 227	
 
Primary objectives
 
1. To determine whether LDLT, which is associated with a regenerating liver, meaningfully increases the incidence of clinical rejection. In the cohort, we will compare the incidence of immunologic complications, specifically the incidence and severity of rejection between LDLT and DDLT in a defined set
 

-	Deviced Calcert Protocol 02100(

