## 4.5.5. 4.5.5 Statistical Analysis

The primary objective is to compare HCV progression probabilities in LDLT versus DDLT, where HCV progression is defined above. This comparison will be tested using logistic regression, with HCV progression (yes/no) at a given time point as the outcome variable, and LDLT versus DDLT as the covariate of interest. This comparison will be adjusted for other variables associated with HCV progression. If HCV progression is evaluated at regular points over time, then discrete time survival analysis will be used to compare the time until HCV progression in the two groups.

1262

1263 Secondary objectives will involve several analyses. First, both the rate of fibrosis 1264 progression (change in Ishak score over time) and change in the necroinflammatory score 1265 (Knodell score) will be analyzed using repeated measures regression. A difference in 1266 slopes of the Ishak or Knodell scores over time for LDLT and DDLT will be tested with 1267 an interaction term between LDLT/DDLT and follow-up time. Second, the proportion of 1268 patients with histologic evidence of recurrent HCV at 3 months and 1 year after LDLT 1269 versus DDLT will be compared using logistic regression. This analysis will parallel the 1270 analysis for the primary objective described above. Because recurrent disease occurs 1271 prior to progressive disease, these two analyses will not be independent. Third, analysis 1272 of viral level at day 7 and months 1, 3, 6, and 12 will be performed using repeated 1273 measures regression, with the primary comparison between LDLT and DDLT. 1274 Differences in the pattern of viral levels over time will be tested using a time by 1275 LDLT/DDLT interaction. As a second step, HCV disease severity will be added to the 1276 model to see if viral level is significantly predicted by disease severity. Fourth, the 1277 incidence of cholestatic hepatitis in LDLT and DDLT will be compared using logistic 1278 regression, adjusted for any other prognostic factors. Finally, graft and patient survival 1279 will be analyzed using Kaplan-Meier estimators, logrank tests comparing LDLT and 1280 DDLT, and Cox regression to compare groups adjusted for other variables.

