## 4.8. Secondary Aim 4: To evaluate differences in the immune response to LDLT vs. DDLT grafts.

1566

Living donor liver transplantation presents a unique immunological setting that is determined by three major variables that are different from the DDLT setting, with the potential to impact on short and long-term graft and patient survival, as well as recurrent disease:

- Regeneration may be associated with different pattern of lymphocyte trafficking in and out of the graft resulting in a differential repopulation of the liver with donor cells, and unknown effects on the extent of peripheral chimerism.
- Transplantation of a lobe from a living donor is done under conditions allowing extremely short cold ischemic time (60 vs. 500 minutes), a variable that may affect the severity of the inflammatory and immune response.
  - 3. We assume that 40% of LDLT are done between genetically related individuals, resulting in a potentially more favorable HLA matching.
- 1578 1579

1577

1580 Preliminary data demonstrate a potentially different alloimmune and antigen-specific 1581 immune response in recipients undergoing LDLT. Previous single center studies have suggested a reduced rate of rejection after adult-to-adult LDLT. Interestingly, there is a 1582 trend toward more rapid recurrence of hepatitis C infection, a phenomenon that may be 1583 1584 related to liver regeneration and/or inhibition of immune related anti-HCV response. The 1585 prospective cohort study will be designed to address whether LDLT affects mechanistic 1586 issues of liver transplantation immunobiology. The clinical findings will be correlated 1587 with specific laboratory assays, and will be compared with a control group undergoing 1588 DDLT transplantation. These findings will determine the opportunities for appropriate 1589 clinical modifications in the immunosuppression protocol, aiming at better outcomes for 1590 graft rejection and reduced frequency of recurrent disease. The clinical data and the 1591 specimens that are collected will be used to further support hypothesis-driven 1592 investigations, aiming to determine patterns of immune response and the potential 1593 development of favorable induction of tolerance, and those that are aiming to reduce the 1594 recurrence of the primary liver disease.

1595

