#### 1656

#### 4.8.4. Sample Size and Power Calculations

1657

Power analyses are based on the proportion of organs that have experienced at least one rejection episode in the first year after transplant, with LDLT and DDLT compared using a test of binomial proportions. We assume 360 LDLT and 355 DDLT patients, two-sided testing and a significance level of 0.05. We will have 93% power to detect a difference between the LDLT and DDLT proportions of 13% (e.g., 43% versus 56%), and will have even greater power if the same 13% difference is closer to zero or one.

1664 **4.8.5. Statistical Analysis** 

1665 The goal of this specific aim is to find predictors of organ rejection, and in particular to 1666 see if rejection rates differ between LDLT and DDLT. We will first use Cox regression, 1667 comparing time from transplant to organ rejection in each group. We will adjust for 1668 patient demographics, recipient and donor ABO and HLA typing, and whether the donor 1669 is related to the recipient. To test the effect of liver regeneration on organ rejection, we

- 1670 will include clinical and biochemical indicators of regeneration in the model.
- 1671 Radiological and pathological correlates, and extent of organ damage will also be tested.
- 1672 We will also consider frequency of rejection in cases of recurrent rejection. If there are
- 1673 enough cases of recurrent rejection, we will compare LDLT with DDLT using a multiple
- 1674 event Cox regression. Severity of rejection in LDLT versus DDLT will also be
- 1675 considered, restricted only to cases with rejection.

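### Controlling the HCV comparison for acute rejection episodes, a post-transplant event that may depend on graft type, yields a direct effect rather than the overall LDLT versus DDLT difference

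*Protocol*

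**What the plan says.** The introduction to Section 4.5 closes by saying that fibrosis and necroinflammatory activity on biopsy will be compared between the graft groups, controlling for factors known to affect "progression (e.g. donor age, acute rejection episodes, baseline viral level". Section 4.5.5 says that the primary comparison, a logistic regression of progression on graft type, will be "adjusted for other variables associated with HCV progression". It names no covariates and sets no limit on when they are measured. Section 4.5 has already listed, among the factors most consistently linked to progressive disease, "pre-transplant level of viremia, absence of HBV coinfection and acute rejection".

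The primary HCV objective in Section 3.5 begins "To determine whether HCV disease progression differs in patients receiving" and sets LDLT against DDLT. It does not ask for an effect with rejection held constant.

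Other sections treat rejection as something graft type may change:
- Section 3.8 asks whether LDLT "meaningfully increases the incidence of clinical rejection".
- Section 4.8 reports that single-center studies "suggested a reduced rate of rejection after adult-to-adult LDLT".
- Section 4.8.4 gives power for a difference "between the LDLT and DDLT proportions of 13% (e.g., 43% versus 56%), and will have" more power nearer the extremes. It does not say which graft has which rate.
- Secondary objective 5 in Section 3.5 compares rejection treatment by graft type in HCV patients and then seeks to "correlate this frequency of treatment of rejection to aggressive recurrence of" HCV.

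**The concern.** Donor age and pre-transplant viral level are fixed before the graft can act, so adjusting for them removes confounding. Acute rejection comes afterwards. If graft type alters rejection and rejection alters HCV progression, rejection lies on the causal path. Conditioning on it removes that part of the graft effect from the LDLT coefficient. It also opens a second route to bias: any unmeasured cause shared by rejection and progression becomes associated with graft type within levels of rejection, even if it was balanced at transplant.

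The result would be read as the answer to the Section 3.5 objective while estimating something else. If LDLT lowers rejection, a real benefit is left out; if LDLT raises it, a real harm is left out. The protocol neither labels the adjusted result a direct effect nor describes a primary model without rejection.

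**Working it through.** **1. The plan's own figures.** Section 4.5.4 gives 107 DDLT and 108 LDLT patients with HCV, one-year progression of 10% versus 25%, and two-sided alpha 0.05.
- Pooled proportion: (107 × 0.10 + 108 × 0.25)/215 = 0.1753.
- SE under the null: √[0.1753 × 0.8247 × (1/107 + 1/108)] = 0.0519.
- SE under the alternative: √[0.10 × 0.90/107 + 0.25 × 0.75/108] = 0.0508.
- Power: Φ[(0.15 − 1.96 × 0.0519)/0.0508] = Φ(0.95) = 0.83, against 82% stated.

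The same formula gives 0.85 for 50% versus 70% (85% stated). For 43% versus 56% rejection with 360 and 355 patients it gives 0.94 (93% stated). The power figures are sound; the issue is the adjustment set.

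**2. The chain in the text.** Rejection is named as a control (Section 4.5) and meets the Section 4.5.5 rule because Section 4.5 lists it as a progression factor. Its dependence on graft type is an open question under study (Sections 3.5, 3.8, 4.8 and 4.8.4). The objective (Section 3.5) is the overall difference.

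**3. Size of the rejection path with no other graft effect.** Let p0 and p1 be the progression risks without and with rejection, linked by an odds ratio OR. Let rD and rL be the rejection rates after DDLT and LDLT. Solve rD × p1 + (1 − rD) × p0 = DDLT progression rate. The LDLT rate is then rL × p1 + (1 − rL) × p0, so the shift is (rL − rD) × (p1 − p0).

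Inputs from the protocol: rejection 43% and 56% (Section 4.8.4), tried in both directions; DDLT progression 10% at one year and 50% at three years (Section 4.5.4). Assumed, because the documents give no figure: OR from 2 to 5.

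Example with OR 2, rD = 0.56, rL = 0.43 and a 10% DDLT rate: p0 = 0.0671 and p1 = 0.1258. The shift is −0.13 × 0.0587 = −0.0076, so the LDLT rate is 9.24%.

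| DDLT rate | OR | LDLT rate if LDLT rejection 43%, DDLT 56% | LDLT rate if LDLT rejection 56%, DDLT 43% |
|---|---|---|---|
| 10% | 2 | 9.24% | 10.82% |
| 10% | 3 | 8.86% | 11.27% |
| 10% | 5 | 8.48% | 11.77% |
| 50% | 2 | 47.8% | 52.2% |
| 50% | 3 | 46.5% | 53.5% |
| 50% | 5 | 45.0% | 55.0% |

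- At 10%: shifts of 0.8 to 1.8 points. Against the 15-point target, 0.76/15 = 5% to 1.77/15 = 12%.
- At 50%: shifts of 2.2 to 5.0 points. Against the 20-point target, 2.23/20 = 11% to 4.95/20 = 25%.

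In this setting the rejection-adjusted graft effect is zero, so adjustment removes the whole shift.

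**4. Direction when there is also a direct effect.** Calibrate the model to the planned 25% versus 10% (overall odds ratio 3.0, difference 0.15), with OR assumed from 1.5 to 5.
- LDLT rejection 43%, DDLT 56%: adjusted odds ratio 3.2 to 4.0, direct risk difference 0.160 to 0.188. Adjustment makes LDLT look worse than it is overall.
- LDLT rejection 56%, DDLT 43%: adjusted odds ratio 2.9 to 2.7, direct risk difference 0.140 to 0.116. Power for a difference of that size falls from 0.83 to between 0.79 and 0.65.

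The risk differences are the better guide to size, since odds ratios also change with adjustment because they are non-collapsible.

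**The case against.** The sentence naming rejection closes an introductory section, introduces its list as examples, and concerns biopsy scores rather than the composite endpoint. The analysis section lists no covariates, and an analysis plan could narrow the set. This stands in part: entry of rejection into the primary progression model is inferred from the rule in Section 4.5.5, not written there. It does not remove a control that the protocol names for the biopsy comparison, or a rule that admits it.

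A reader might infer that the protocol expects rejection to differ by graft type. It does not go that far: Section 3.8 poses a question, Section 4.8 reports a suggestion from earlier studies in the opposite direction, and the 43%/56% pair is an example without assigned groups.

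A reader might also infer that adjustment necessarily shrinks the LDLT effect. It need not: with more HCV harm but less rejection after LDLT, adjustment enlarges it.

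The one-year shift is small: 0.8 to 1.8 points against a standard error of about 5 points. An effect net of rejection is also a legitimate question, and secondary objective 5 would bring the rejection route partly into view. These points limit the weight of the concern. They do not make an unlabelled direct effect an answer to the stated objective.

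Finally, the endpoint definition in Section 4.5.1 and the evaluable-biopsy rule in Section 4.5.3 already require rejection to be absent. Deleting the covariate therefore does not fully restore the overall effect. That is correct and is carried into the fix.

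**Conclusion.** The concern holds in a limited form. As written, the plan controls the HCV biopsy comparison for a post-transplant event that may be caused by graft type, and its general rule would carry that event into the primary progression model. The resulting coefficient is a direct effect open to collider bias, and the bias may run in either direction. The change is worth making, but the concern does not call the aim as a whole into question.

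The sizes in the working rest on four assumptions: a rejection-progression odds ratio of 2 to 5, all-recipient rejection rates applied to HCV patients (who have their own prednisone schedule in Section 4.8.1), either direction of the rejection difference, and no other graft effect. They cover the rejection path only; the collider component cannot be sized from the documents.

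**What to change.** In Sections 4.5 and 4.5.5, adjust the main LDLT versus DDLT contrast only for variables fixed at or before transplant, such as donor age, pre-transplant viral level, year of transplant and HBV coinfection. Delete acute rejection episodes from that set. Report any model that adds rejection as a secondary analysis, labelled as a direct-effect estimate.

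State that the absence-of-rejection condition on the endpoint (Section 4.5.1) and on evaluable biopsies (Section 4.5.3) still conditions on rejection, and report by graft type how many biopsies it excludes.

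The cost is a few sentences in the protocol or analysis plan and one extra table. No new data are needed, since rejection episodes and biopsies are already collected (Section 4.8.3), and no clinical rule changes.
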